8.1.4 In-Text Summaries

In-text Tables 11.3.1(a)(b)(c)(d) will summarize the antibody response from baseline to the post dose 2 (Day 19) time point and the GMT and 95% CI of GMT at the post dose 2 (Day 19) time point by treatment group and antigen strain for the ALS assay. In addition, the number of antigens where an antibody response is observed at the post dose 2 (Day 19) time point will be calculated per participant. The five primary antigens will be LTB, CFA/I, CS3, CS5 and CS6. If a participant has specimen results for all 5 antigens at both baseline and post dose 2 (Day 19), they will be included in a summary presented as Table 11.3.2.1 (a)(b)(c)(d). An analysis of variance will be used to determine if the number of antigens responding is different between treatment groups.

Additional tables will be created following the same structure and analyses as above for the following groups:

• Participants with specimen results for at least 4 antigens at both baseline and post dose 2 (Day 19), Table 11.3.2.2 (a)(b)(c)(d).

- Participants with specimen results for at least 3 antigens at both baseline and post dose 2 (Day 19), Table 11.3.2.3 (a)(b)(c)(d).
- Participants with specimen results for at least 2 antigens at both baseline and post dose 2 (Day 19), Table 11.3.2.4 (a)(b)(c)(d).

8.2 Fecal Antibodies

Immune responses as measured by Fecal SIgA after each dose (Day 7 and Day 19 samples) and at Day 29 will be evaluated by the following:

- the proportion of participants achieving an antibody response after the first vaccination (i.e., antibody response is calculated using baseline and Day 7 sample) for CFA/I, CS3, CS5, CS6, LTB and 078 LPS (if sample available);
- the proportion of participants achieving an antibody response after the second vaccination (i.e., antibody response is calculated using baseline and Day 19 sample) for CFA/I, CS3, CS5, CS6, LTB and 078 LPS (if sample available);
- the proportion of participants achieving an antibody response after the second vaccination at Day 29 (i.e., antibody response is calculated using baseline and Day 29 sample) for CFA/I, CS3, CS5, CS6, LTB and 078 LPS (if sample available);
- the proportion of participants achieving an antibody response after either vaccination (i.e., antibody response observed after either vaccination) for CFA/I, CS3, CS5, CS6, LTB and 078 LPS (if sample available);
- the geometric mean titer (GMT) of CFA/I, CS3, CS5, CS6, LTB, and 078 LPS (if sample available) at screening, after the first dose (Day 7), after the second dose (Day 19) and after the second dose (Day 29);
- the geometric mean fold rise (GMFR) of CFA/I, CS3, CS5, CS6, LTB and 078 LPS(if sample available) between doses (baseline to post-dose 1 and post-dose 1 to post-dose 2 [Day 19]), from baseline to post-dose 2 (Day 19), and from baseline to post-dose 2 (Day 29).

8.2.1 Antibody response

Percentages of participants with an antibody response at Day 7, Day 19, Day 29 or at any time point will be calculated along with the corresponding two-sided exact (Clopper-Pearson) binomial 95% CIs. For each antigen, the proportion of participants with an antibody response at Day 7, Day 19, Day 29 or at any time point will be compared between each pairwise comparison of ETVAX dose level, ETVAX + dmLT dose level, and placebo using Fisher's exact test.

Tables 14.2.8.1 (a)(b)(c)(d) - 14.2.8.2 (a)(b)(c)(d) will summarize the antibody response and 95% CIs for each time period and treatment group by antigen for the FA population and the PP population, respectively. In addition, a Fisher's exact test for each treatment group comparison will be presented for each time period and antigen as shown in Tables 14.2.9.1 (a)(b)(c)(d) - 14.2.9.2(a)(b)(c)(d) for the FA population and the PP population, respectively.

8.2.2 Geometric Mean Titer

For the Fecal SIgA titers, antibody levels will be summarized on the original scale by treatment group at Screening, Day 7, Day 19 and Day 29. The number of observations, geometric mean titer (GMT) and geometric 95% CI of the GMT will be reported. For Fecal titers below the LLoQ, an arbitrary value of half of the LLoQ will be used. The GMT will be calculated as the antilog of the mean of the logarithms of the Fecal titer. The 95% CIs of the GMT will be based on the t-distribution to provide population estimates and will be presented as the antilog. Two-sided 95% CIs for the ratios of post dose 1 and post dose 2 GMTs between two treatment groups will be constructed using the log normal distribution. The log values will be used to construct a CI using the t-distribution for the mean difference between all pair-wise comparisons. The mean difference and the corresponding CI limits will then be exponentiated to obtain the GMT ratio and the corresponding CI. Each pairwise comparison will be performed on the log-normal assay responses using a t-test. If the values deviate from the log normal distribution, a non-parametric method (i.e., Wilcoxon) may be used for the analysis of the ratio of GMT.

Tables 14.2.10.1 (a)(b)(c)(d) - 14.2.10.2 (a)(b)(c)(d) will summarize the GMTs and 95% CIs for each antigen and treatment group for the FA population and the PP population, respectively. The ratio of GMTs, 95% CI of ratio of GMTs and t-test will be summarized in Tables 14.2.11.1 (a)(b)(c)(d) - 14.2.11.2 (a)(b)(c)(d). Reverse cumulative distribution curves for the ALS titer after the first vaccination (Day 7) and the second vaccination (Day 19 and Day 29) will be presented by treatment group for each antigen analyzed as depicted in Figures 14.2.12.1 (a)(b)(c)(d) - 14.2.12.2 (a)(b)(c)(d).

8.2.3 Geometric Mean Fold Rise

For the Fecal SIgA titer, the fold rise will be calculated after the first vaccination (post vaccination 1 (Day 7) antibody titer/baseline antibody titer), after the second vaccination (post vaccination 2 (Day 19) antibody titer/baseline antibody titer), after the second vaccination (post vaccination 2 (Day 29) antibody titer/baseline antibody titer), and after the second vaccination compared to first vaccination (post vaccination 2 (Day 19) antibody titer/post vaccination 1 (Day 7) antibody titer). The number of observations, GMFR and 95% confidence intervals for the GMFR will be reported. The GMFR will be calculated as the antilog of the mean of the logarithms of the calculated fold rise. The 95% CIs for the GMFR will be based on the t-distribution to provide population estimates and will be presented as the antilog. Pairwise comparisons of the logs of the fold-rise will be performed using a t-test. If the values deviate from the log normal distribution, a non-parametric method (i.e., Wilcoxon) may be used for the analysis of the fold rise.

Tables 14.2.13.1 (a)(b)(c)(d) - 14.2.13.2 (a)(b)(c)(d) will summarize the GMFRs and 95% CIs for the GMFRs for each antigen and treatment group for the FA population and the PP population, respectively. In addition, the p-value from a t-test for each treatment group comparison will be presented for each time period and antigen as shown in Tables 14.2.14.1 (a)(b)(c)(d) - 14.2.14.2(a)(b)(c)(d) for the FA population and the PP population, respectively.

8.2.4 In-Text Summaries

In-text Tables 11.3.3(a)(b)(c)(d) will summarize the antibody response from baseline to the post dose 2 (Day 19) time point and the GMT and 95% CI of GMT at the post dose 2 (Day 19) time point by treatment group and antigen strain for the fecal secretion assay. In addition, the number of antigens where an antibody response is observed at the post dose 2 (Day 19) time point will be calculated per participant. The five primary antigens will be LTB, CFA/I, CS3, CS5 and CS6. If a participant has specimen results for all 5 antigens at both baseline and post dose 2 (Day 19), they will be included in summary presented on Table 11.3.4 (a)(b)(c)(d). A Fisher's exact test will be used to compare each vaccine treatment against placebo.

The comparisons will be:

- the number of participants with 5 antigens responding versus those with 4 or less responding,
- the number of participants with 4 or more antigens responding versus those with 3 or less responding,
- the number of participants with 3 or more antigens responding versus those with 2 or less responding,
- the number of participants with 2 or more antigens responding versus those with 1 or less responding, and
- the number of participants with 1 or more antigens responding versus those with no antigens responding.

8.3 Plasma ELISA Antibodies

For ELISA IgA, tables will be presented by antigen in the order of priority as specimen volumes allow. The order of the antigens will be: LTB, 078 LPS, CFA/I, CS3, CS6, and CS5. For ELISA IgG, only LTB and 078S LPS will be analyzed. Immune responses as measured by ELISA IgA and IgG after each vaccination (Day 7 and Day 19 samples) will be evaluated by the following:

- the percentage of participants achieving an IgA antibody response after the first vaccination (i.e., antibody response is calculated using baseline and Day 7 sample) for LTB, 078 LPS, CFA/I, CS3, CS6, and CS5;
- the percentage of participants achieving an IgA antibody response after the second vaccination (i.e., antibody response is calculated using baseline and Day 19 sample) for LTB, 078 LPS, CFA/I, CS3, CS6, and CS5;
- the percentage of participants achieving an IgA antibody response after either vaccination (i.e., antibody response observed after either vaccination) for LTB, 078 LPS, CFA/I, CS3, CS6, and CS5;
- the IgA geometric mean titer (GMT) of LTB, 078 LPS, CFA/I, CS3, CS6, and CS5 at screening and after each vaccination;
- the IgA geometric mean fold rise(GMFR) of LTB, 078 LPS, CFA/I, CS3, CS6, and CS5 between doses (baseline to post-dose 1 and post-dose 1 to post-dose 2) and from baseline to post-dose 2.

- the percentage of participants achieving an IgG antibody response after the first vaccination (i.e., antibody response is calculated using baseline and Day 7 sample) for LTB and 078 LPS (if sample available);
- the percentage of participants achieving an IgG antibody response after the second vaccination (i.e., antibody response is calculated using baseline and Day 19 sample) for LTB and 078 LPS;
- the percentage of participants achieving an IgG antibody response after either vaccination (i.e., antibody response observed after either vaccination) for LTB and 078 LPS;
- the IgG geometric mean titer (GMT) of LTB and 078 LPS at screening and after each vaccination;
- the IgG geometric mean fold rise(GMFR) of LTB and 078 LPS between doses (baseline to post-dose 1 and post-dose 1 to post-dose 2) and from baseline to post-dose 2.

8.3.1 Antibody response

Percentages of participants with an antibody response at Day 7, Day 19 or at any time point will be calculated along with the corresponding two-sided exact (Clopper-Pearson) binomial 95% CIs. For each antigen, the proportion of participants with an antibody response at Day 7, Day 19 or at any time point will be compared between each pairwise comparison of ETVAX dose level, ETVAX + dmLT dose level, and placebo using Fisher's exact test.

Tables 14.2.15.1 (a)(b)(c)(d) - 14.2.15.2 (a)(b)(c)(d) for IgA and Tables 14.2.17.1(a)(b)(c)(d) - 14.2.17.2 (a)(b)(c)(d) for IgG will summarize the antibody response and 95% CIs for each time period and treatment group by antigen for the FA population and the PP population, respectively. In addition, a Fisher's exact test for each treatment group comparison will be presented for each time period and antigen as shown for IgA in Tables 14.2.16.1 (a)(b)(c)(d) - 14.2.16.2(a)(b)(c)(d) and for IgG in Tables 14.2.18.1 (a)(b)(c)(d) - 14.2.18.2(a)(b)(c)(d) for the FA population and the PP population, respectively.

8.3.2 Geometric Mean Titer

For the ALS titer, antibody levels will be summarized on the original scale by treatment group at Screening, Day 7 and Day 19. The number of observations, geometric mean titer (GMT) and geometric 95% CI of the GMT will be reported. For ALS titers below the LLoQ, an arbitrary value of half of the LLoQ will be used. The GMT will be calculated as the antilog of the mean of the logarithms of the ALS titer. The 95% CIs of the GMT will be based on the t-distribution to provide population estimates and will be presented as the antilog. Two-sided 95% CIs for the ratios of post dose 1 and post dose 2 GMTs between two treatment groups will be constructed using the log normal distribution. The log values will be used to construct a CI using the t-distribution for the mean difference between all pair-wise comparisons. The mean difference and the corresponding CI limits will then be exponentiated to obtain the GMT ratio and the corresponding CI. Each pairwise comparison will be performed on the log-normal assay responses using a t-test. If the values deviate from the log normal distribution, a non-parametric method (i.e., Wilcoxon) may be used for the analysis of the ratio of GMT.

Tables 14.2.19.1 (a)(b)(c)(d) - 14.2.19.2 (a)(b)(c)(d) for IgA and Tables 14.2.21.1 (a)(b)(c)(d) - 14.2.21.2 (a)(b)(c)(d) for IgG will summarize the GMTs and 95% CIs for each antigen and treatment group for the FA population and the PP population, respectively. The ratio of GMTs, 95% CI of ratio of GMTs and t-test will be summarized in Tables 14.2.20.1 (a)(b)(c)(d) - 14.2.20.2 (a)(b)(c)(d) for IgA and

Tables 14.2.22.1 (a)(b)(c)(d) - 14.2.22.2 (a)(b)(c)(d) for IgG. Reverse cumulative distribution curves for the ELISA titer after the first vaccination (Day 7) and the second vaccination (Day 19) will be presented by treatment group for each antigen analyzed as depicted in Figures 14.2.23.1 (a)(b)(c)(d) - 14.2.23.2 (a)(b)(c)(d) for IgA and Tables 14.2.24.1 (a)(b)(c)(d) - 14.2.24.2 (a)(b)(c)(d) for IgG.

8.3.3 Geometric Mean Fold Rise

For the ELISA titer, the fold rise will be calculated after the first vaccination (post vaccination 1 antibody titer/baseline antibody titer), after the second vaccination (post vaccination 2 antibody titer/baseline antibody titer), and after the second vaccination compared to first vaccination (post vaccination 2 antibody titer/post vaccination 1 antibody titer). The number of observations, GMFR and 95% confidence intervals for the GMFR will be reported. The GMFR will be calculated as the antilog of the mean of the logarithms of the calculated fold rise. The 95% CIs for the GMFR will be based on the t-distribution to provide population estimates and will be presented as the antilog. Pairwise comparisons of the logs of the fold-rise will be performed using a t-test. If the values deviate from the log normal distribution, a non-parametric method (i.e., Wilcoxon) may be used for the analysis of the fold rise.

Tables 14.2.25.1 (a)(b)(c)(d) - 14.2.25.2 (a)(b)(c)(d) for IgA and Tables 14.2.27.1(a)(b)(c)(d) - 14.2.27.2 (a)(b)(c)(d) for IgG will summarize the GMFRs and 95% CIs for the GMFRs for each antigen and treatment group for the FA population and the PP population, respectively. In addition, the p-value from a t-test for each treatment group comparison will be presented for each time period and antigen as shown in Tables 14.2.26.1 (a)(b)(c)(d) - 14.2.26.2(a)(b)(c)(d) for IgA and Tables 14.2.28.1 (a)(b)(c)(d) - 14.2.28.2(a)(b)(c)(d) for IgG for the FA population and the PP population, respectively.

8.3.4 In-text summaries

In-text Tables 11.3.5(a)(b)(c)(d) will summarize the antibody response from baseline to the post dose 2 (Day 19) time point and the GMT and 95% CI of GMT at the post dose 2 (Day 19) time point by treatment group and antigen strain for the plasma ELISA IgA assay. In addition, the number of antigens where an antibody response is observed at the post dose 2 (Day 19) time point will be calculated per participant. The five primary antigens will be LTB, CFA/I, CS3, CS5 and CS6. If a participant has specimen results for all 5 antigens at both baseline and post dose 2 (Day 19), they will be included in summary presented on Table 11.3.6 (a)(b)(c)(d). A Fisher's exact test will be used to compare each vaccine treatment against placebo.

The comparisons will be:

- the number of participants with 5 antigens responding versus those with 4 or less responding,
- the number of participants with 4 or more antigens responding versus those with 3 or less responding,
- the number of participants with 3 or more antigens responding versus those with 2 or less responding,
- the number of participants with 2 or more antigens responding versus those with 1 or less responding,
- the number of participants with 1 or more antigens responding versus those with 0 antigens responding.

8.4 T-cell Immune Responses

Individual T-cell and other immune responses will be listed by participant and antigen in Listings 16.2.6.4(a)(b)(c)(d). A more detailed description of analyses will be provided after it is known if and what specimens will be available for analysis.

9 SAFETY EVALUATION

9.1 Adverse Events

All safety analyses will be presented using the Safety population.

Any medical condition that is present at the time that the participant is screened will be considered baseline and not reported as an AE, unless it worsens in severity or increases in frequency during the study. When calculating the incidence of solicited and unsolicited adverse events (i.e., on a per participant basis), each participant will be counted once and any repetitions of solicited and unsolicited adverse events within a participant will be ignored; the denominator will be the total population size. All adverse events reported will be included in the summaries and analyses.

9.1.1 Solicited Events and Symptoms

Solicited adverse events will be collected pre-vaccination, 60 minutes post-vaccination and then daily for 7 days after vaccination and graded on a scale of 0 (absent), 1 (mild), 2 (moderate) and 3 (severe). Solicited events include: elevated oral temperature, nausea, vomiting, loose stools, diarrhea, abdominal pain/stomach ache, and acute systemic allergic reaction. Adults will have all events collected. Toddlers (24 - 59 months) will have all events except nausea collected and Younger Children (12 - 23 Months) and Infants (6 - 11 months) will only have oral temperature, vomiting, loose stools, diarrhea and acute systemic allergic reaction collected.

The proportion of participants reporting at least one solicited adverse event within 7 days of any vaccination will be summarized for each solicited adverse event and for any solicited adverse event. The 95% CI calculated using Clopper-Pearson methodology from a binomial distribution (SAS Proc Freq with a binomial option) will be presented (Tables 14.3.1.1(a)(b)(c)(d)).

For each solicited adverse event and for any solicited adverse event, the maximum severity over 7 days after each vaccination will be summarized for the Safety population. The number and percentage of participants reporting each event will be summarized for each treatment group by the maximum severity. For each event the denominator is the number of participants with non-missing data for the specific event (Tables 14.3.1.2(a)(b)(c)(d)).

The number and percentage of participants reporting any solicited adverse event and reporting each individual solicited adverse event will be summarized for each day post vaccination for each vaccination by Treatment group (Tables 14.3.1.3(a)(b)(c)(d)) and severity. The percent of participants reporting any solicited event will be displayed graphically in a bar chart in Figures 14.3.1.4(a)(b)(c)(d)).

Fisher's exact test will be used to compare the proportion of participants with solicited reactogenicity events between each of the vaccine arms with the placebo arms. In addition, the vaccine arms without dmLT will be combined, the vaccine arms with dmLT will be combined and all vaccine arms will be combined and each will be compared to placebo. The results will be summarized in Tables 14.3.1.5(a)(b)(c)(d).

A logistic regression analysis will be presented to look at the proportion of vomiting after any ETVAX dose, with covariates for sex, age group (i.e., cohort's B, C and D), dose and adjuvant in the model. The age group categories will correspond with cohorts B, C and D: 6-11 months, 12-23 months, and 24-59 months, respectively. Results will be summarized for all vaccinated children in Table 14.3.1.6.1 and all children in Table 14.3.1.6.2.

The primary purpose of the statistical comparisons is to screen out potential solicited reactogenicity events that need further clinical evaluation. Therefore, they are not considered formal statistical hypothesis tests and it is acknowledged that there will be inflated Type I errors (i.e., inflated false statistical significances) from performing multiple unadjusted comparisons.

Solicited adverse events by participant will be presented in Listings 16.2.7.1(a)(b)(c)(d).

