3.2 Endpoints

3.2.1 Primary Endpoints

The primary endpoints deal with safety and tolerability and are the following:

- Proportion (%) of SAEs
- Proportion (%) of AEs
- Proportion (%) of vaccine induced reactogenicity events

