6 GENERAL STATISTICAL CONSIDERATIONS

6.1 General Principles

All continuous variables will be summarized using the following descriptive statistics: n (non-missing sample size), mean, standard deviation, median, quartiles and range (maximum and minimum). Where appropriate (e.g., immunogenicity), geometric means and corresponding 95% confidence intervals will be included. The number and percent of participants (based on the population sample size) of observed levels will be reported for all categorical measures. Where appropriate (e.g., immunogenicity and safety outcomes), 95% confidence intervals for the proportion of participants with an event will be included.

In general, all data will be listed, sorted by treatment and participant, and when appropriate by visit number within participant. All summary tables will be structured with a column for each treatment in the order of non-adjuvanted ETVAX, low dose adjuvanted ETVAX, medium dose adjuvanted ETVAX, high dose adjuvanted ETVAX and Placebo and will be annotated with the total population size relevant to specific tables/treatment, including any missing observations.

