6.3.2 Safety Population

All participants in the enrolled population who receive a study vaccination and have safety data available will be included in the safety population. Treatment groups for safety analysis will be assigned according to the actual treatment received at the first vaccination. If a participant receives mixed doses (e.g., an ETVAX dose without dmLT at Dose 1 and the same ETVAX at Dose 2 with dmLT), the safety data collected after the start of the mixed dosing (e.g., post Dose 2) will be excluded from the analysis. All excluded data will be presented in the data listings. All safety analyses will be performed using this population.

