Symptom	n	%	(95% CI)	n	%	(95% CI)	n	%	(95% CI)	n	%	(95% CI)	n	%	(95% CI)
Elevated oral temperature															
Vomiting															
Loose stools															
Diarrhea															
Abdominal pain/stomach ache															
Acute systemic allergic reaction															
Any Symptom															

N = Number of participants in the Safety population.

TABLE 14.3.1.1(c):
Number and Percentage of Participants Experiencing Solicited Events with
95% Confidence Intervals by Symptom and Treatment Group - Young Children (12 - 23 Months)

		Placebo (N=XX)				(1/4 Dose =XX)			X 1/2 Dose =XX)		ETV	mbined AX Alone N=XX)
Symptom	n	% (95% CI) n			%	(95% CI)	n	%	(95% CI)	n	%	(95% CI)
Elevated oral temperature												
Vomiting												
Loose stools												
Diarrhea												
Acute systemic allergic reaction												
Any Symptom												

	(+ 2.5 μg dmLT (N=XX)		(h	ighest +5 μg	VAX safe dose) g dmLT =XX)		ETVAX	abined X + dmLT =XX)			nrticipants N=XX)
Symptom	n	% (95% CI) n			%	(95% CI)	n	%	(95% CI)	n	%	(95% CI)
Elevated oral temperature												
Vomiting												
Loose stools												
Diarrhea												
Acute systemic allergic reaction												
Any Symptom												

N = number of participants in the Safety population.

TABLE 14.3.1.1(d):
Number and Percentage of Participants Experiencing Solicited Events with
95% Confidence Intervals by Symptom and Treatment Group - Infants (6 - 11 Months)

			cebo XX)	ETVAX 1/8 Dose (N=XX) (N=XX)]		X 1/2 Dose N=XX)	C	A	ed ETVAX lone =XX)			
Symptom	n	%	(95% CI)	n	%	(95% CI)	n	%	(95% CI)	n	%	(95% CI)	n	%	(95% CI)
Elevated oral temperature															
Vomiting															
Loose stools															
Diarrhea															
Acute systemic allergic reaction															
Any Symptom															

	(highest + 2.5 μ	VAX safe dose) g dmLT =XX)		ighest +5 μg	VAX safe dose) g dmLT =XX)		ETVAX	nbined K + dmLT =XX)			articipants N=XX)
Symptom	n	n % (95% CI) n		n	%	(95% CI)	n	%	(95% CI)	n	%	(95% CI)
Elevated oral temperature												
Vomiting												
Loose stools												
Diarrhea												
Acute systemic allergic reaction												
Any Symptom												

N = number of participants in the Safety population.

TABLE 14.3.1.2(a): Number and Percentage of Participants Experiencing Solicited Events by Symptom, Maximum Severity and Treatment Group - Adults

			acebo =XX)		Full Dose =XX)	ETVAX 1 + 10 μg (N=	dmLT	All Part (N=	icipants XX)
Symptom	Severity	n	%	n	%	n	%	n	%

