Any Symptom	None								
	Mild								
	Moderate								
	Severe								
Elevated oral temperature	None								
	Mild								
	Moderate								
	Severe								
Nausea	None								
	Mild								
	Moderate								
	Severe								
Vomiting	None								
	Mild								
	Moderate								
	Severe								
Loose stools	None								
	Mild								
	Moderate								
	Severe								

TABLE 14.3.1.2(a): continued Number and Percentage of Participants Experiencing Solicited Events by Symptom, Maximum Severity and Treatment Group - Adults

			acebo =XX)		Full Dose =XX)	ETVAX 1 + 10 μg (N=	dmLT		icipants XX)
Symptom	Severity	n	%	n	%	n	%	n	%
Diarrhea	None								
	Mild								
	Moderate								
	Severe								
Abdominal pain/stomach ache	None								
	Mild								
	Moderate								
	Severe								
Acute systemic allergic reaction	None								
	Mild								
	Moderate								
	Severe								

N = Number of participants in the Safety population; Severity is based off of the maximum severity reported post vaccination.

TABLE 14.3.1.2(b):
Number and Percentage of Participants Experiencing Solicited Events by
Symptom, Maximum Severity and Treatment Group - Toddlers (24 - 59 Months)

			acebo (=XX)	ETV 1/4 I (N=	Dose	ETVAX (N=)			Full Dose -XX)	Combined ETVA (N=XX)	
Symptom	Severity	n	%	n	%	n	%	n	%	n	%
Any Symptom	None										
	Mild										
	Moderate										
	Severe										
Elevated oral temperature	None										
	Mild										
	Moderate										
	Severe										
Vomiting	None										
	Mild										
	Moderate										
	Severe										
Loose stools	None										
	Mild										
	Moderate										
	Severe										
Diarrhea	None										
	Mild										
	Moderate										
	Severe										
Abdominal pain/stomach ache	None										
	Mild										
	Moderate										
	Severe										
Acute systemic allergic reaction	None										
	Mild										
	Moderate										
	Severe										

N = Number of participants in the Safety population; Severity is based off of the maximum severity reported post vaccination.

TABLE 14.3.1.2(b): continued Number and Percentage of Participants Experiencing Solicited Events by Symptom, Maximum Severity and Treatment Group - Toddlers (24 - 59 Months)

		(highest + 2.5 µ	VAX safe dose) ug dmLT =XX)	(highes + 5 μ	TVAX t safe dose) ag dmLT	ETV (highest s + 10 µg (N=	afe dose) dmLT	ETVAX	bined + dmLT -XX)		ticipants XX)
Symptom	Severity	n	%	n	%	n	%	n	%	n	%
Any Symptom	None										
	Mild										
	Moderate										
	Severe										

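### Sections 9.1 and 9.1.1 of the SAP give different denominators for solicited events, so Tables 14.3.1.1 and 14.3.1.5 need not agree with Table 14.3.1.2 once anyone lacks solicited data

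*SAP*

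**What the plan says.** The primary endpoints in section 3.2.1 include "Proportion (%) of vaccine induced reactogenicity events".

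- **Section 9.1** covers the per-participant incidence of both solicited and unsolicited events and says that "the denominator will be the total population size".
- **Section 6.1** agrees in general terms: "The number and percent of participants (based on the population sample size) of observed levels will be reported for all categorical measures".
- **Section 9.1.1, Tables 14.3.1.1:** "The proportion of participants reporting at least one solicited adverse event within 7 days of any vaccination will be summarized", with Clopper-Pearson intervals. This paragraph names no denominator. The shells carry the note "N = Number of participants in the Safety population".
- **Section 9.1.1, Tables 14.3.1.2** (maximum severity): "For each event the denominator is the number of participants with non-missing data for the specific event". The shells say something else: "N = Number of participants in the Safety population; Severity is based off of the maximum severity reported post vaccination". Their rows are None, Mild, Moderate and Severe only.
- **Section 9.1.1, Tables 14.3.1.5** (Fisher's exact tests against placebo): no denominator is named in the text, and N in the shells is the Safety population.
- **Section 6.5:** missing solicited data are not imputed and are to appear as not reported. Of the tables discussed here, only the daily Tables 14.3.1.3 have a row for that.

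**The concern.** Tables 14.3.1.1, 14.3.1.2 and 14.3.1.5 rest on the same fact for each participant: whether a given solicited event occurred after vaccination. Two denominators for that fact can give two percentages in neighbouring tables. For 14.3.1.2 itself, a programmer who follows the text and one who follows the shell would produce different numbers.

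Under the total-population rule, someone with no data for an event is counted in N and cannot be counted in n. That is arithmetically the same as being event-free, although the SAP never says such participants should be treated so. The percentage in 14.3.1.1 and 14.3.1.5 is then the lowest value compatible with the data. This matters because the endpoint is primary, the planned arms are small (15, or 30 for infants, section 5), and section 9.1.1 gives the Fisher tests the job of flagging events for clinical evaluation.

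**Working it through.** **The plan's own figures.** The SAP gives no figure for the solicited-event denominator. The nearest denominator-dependent figures are the zero-event bounds for serious adverse events in section 5. The one-sided 95% upper bound is 1 − 0.05^(1/n), which gives 18.1% for n = 15 and 9.5% for n = 30. Both match the plan. They say nothing about missing solicited data.

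**Which rule governs which table**

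| Table | Denominator in text | N in shell | Not-reported row |
|---|---|---|---|
| 14.3.1.1 | none of its own; 9.1 applies (total) | Safety population | no |
| 14.3.1.2 | non-missing for the event (9.1.1) | Safety population | no |
| 14.3.1.3 | none of its own; 9.1 applies (total) | Safety population, plus an N for each day | yes |
| 14.3.1.5 | none of its own; 9.1 applies (total) | Safety population | no |

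**Inputs.** N is the planned group size from section 5. The event count x and the number m with no solicited data for that event after any dose are not in the SAP. The range m = 0 to 3 is an assumption.

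**Formulae.** Total-population rule: x/N. Non-missing rule: x/(N − m). With m = 0 the two are equal. With m > 0 and x > 0 the first is always the smaller.

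| N, x | x/N | m = 1 | m = 2 | m = 3 |
|---|---|---|---|---|
| 15, 3 | 20.0% | 3/14 = 21.4% | 3/13 = 23.1% | 3/12 = 25.0% |
| 15, 6 | 40.0% | 6/14 = 42.9% | 6/13 = 46.2% | 6/12 = 50.0% |
| 30, 6 | 20.0% | 6/29 = 20.7% | 6/28 = 21.4% | 6/27 = 22.2% |

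The Clopper-Pearson 95% interval is 4.3% to 48.1% for 3/15 and 5.5% to 57.2% for 3/12.

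**Consistency between tables.** As the shells are laid out, 100% minus None in 14.3.1.2 should equal the incidence in 14.3.1.1. With 1 to 3 unobserved, the gap is 1.4 to 5.0 points at 3/15, 2.9 to 10.0 points at 6/15, and 0.7 to 2.2 points at 6/30.

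**Effect on a Fisher comparison.** Take the planned toddler placebo total of 6 × 10 = 60 (section 4.3). Comparing 3/15 with 2/60 gives p = 0.052; comparing 3/14 with 2/60 gives p = 0.044. The counts were chosen to show that one unobserved vaccinee can move a result across 0.05. They are not a forecast.

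**The case against.** The strongest defence is that section 9.1.1 is a specific exception to a general rule, and that section 6.1 lets a header N include missing observations while percentages use another base. That reading is possible for Tables 14.3.1.2 alone. It does not explain why the same participant-level fact has one base there and another in 14.3.1.1 and 14.3.1.5, and it leaves all three without the not-reported summary that section 6.5 promises.

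The defence is right that the affected group is probably small. Solicited events are assessed at 60 minutes and then daily, by interview, memory aid and clinic assessment (sections 4.5.1.1 and 9.1.1), so a lost diary alone does not leave a participant unobserved. The Fisher tests are also declared not to be formal hypothesis tests.

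A reader might infer more than the document supports:

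- **That the daily tables have the same fault.** They do not. Tables 14.3.1.3 separate Not Reported from None and give a day-specific N.
- **That missing dose-2 data dilute the primary proportion.** Section 6.3.2 says that after mixed dosing "the safety data collected after the start of the mixed dosing (e.g., post Dose 2) will be excluded from the analysis". But Tables 14.3.1.1 count events after any vaccination, and the shells of 14.3.1.5 have no dose-2 column. Someone missing only dose-2 data who has dose-1 assessments is still observed there.
- **That the bias is concentrated in the highest-dose arms.** The notes to Tables 14.3.1.6.1 and 14.3.1.6.2 record five full-dose recipients. The SAP does not say that their second doses were withheld or that their solicited data are missing. Groups follow the treatment received at the first vaccination, so five recipients give N = 5, not a group of 15 with ten unobserved.

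**Conclusion.** The concern holds in this limited form. Two denominator rules for solicited events stand in the current text, and the shells of 14.3.1.2 contradict the rule written for them. In Tables 14.3.1.1 and 14.3.1.5, a participant with no solicited data for an event after any dose lowers the reported percentage relative to the observed-data percentage, provided at least one event occurred in the group.

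The size depends on missingness that the SAP does not give. With 1 to 3 unobserved of 15 and 3 events, 20.0% becomes 21.4% to 25.0%. In infant groups of 30 the shift is smaller, and with complete data it is zero. The lowering is within an arm. The effect on a vaccine–placebo difference also depends on how many placebo participants are unobserved. The observed-data percentage itself assumes that unobserved participants resemble the observed ones, which is why the not-reported count should be shown beside it.

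This should be corrected before the tables are programmed, because it concerns a primary endpoint and costs little. It does not show that the trial's reactogenicity results are biased.

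**What to change.** 1. Use one denominator in Tables 14.3.1.1, 14.3.1.2 and 14.3.1.5: participants who received at least one dose and have at least one post-dose solicited assessment for that event retained under section 6.3.2.
2. For any by-dose summary, use participants who received that dose and have a retained assessment after it.
3. Print that N in the shells in place of the Safety-population N, and add a not-reported count to each of the three.
4. Limit the total-population rule in section 9.1 to unsolicited adverse events.

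The cost is minor edits to the SAP text and shells, with no new data. Some reported percentages will become slightly less favourable to the vaccine.
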